12.4 Response Criteria

12.4.1 Evaluation of Target Lesions

Complete Response (CR):	Disappearance of all target lesions. Lymph node CR is when the lymph node has decreased to less than 10mm in the short axis.
Partial Response (PR):	At least a 30% decrease in the sum of the longest diameter (LD) of target lesions, taking as reference the baseline sum LD
Progressive Disease (PD):	At least a 20% increase in the sum of the LD of target lesions, taking as reference the smallest sum LD recorded since the treatment started (including the baseline scan if that is the smallest), and at least a 5mm increase or the appearance of new lesions.
Stable Disease (SD):	Neither sufficient shrinkage to qualify for PR nor sufficient increase to qualify for PD, taking as reference the smallest sum LD since the treatment started.

12.4.2 Evaluation of Non-Target Lesions

Complete Response (CR):	Disappearance of all non-target lesions and normalization of tumor marker level. Note: If tumor markers are initially above the upper normal limit, they must normalize for a patient to be considered in complete clinical response.
Incomplete Response/Stable Disease (SD):	Persistence of one or more non-target lesion(s) and/or maintenance of tumor marker level above the normal limits.
Progressive Disease (PD):	Appearance of one or more new lesions and/or unequivocal progression of existing non-target lesions. However, unequivocal progression should not normally trump target disease status. It must be representative of overall disease status change, not a single lesion increase.

Although a clear progression of “non-target” lesions only is exceptional, the opinion of the treating physician should prevail in such circumstances.

12.5. Duration of Response

All response measurements will be from start of treatment to the defined endpoint.

13 STATISTICAL CONSIDERATIONS

13.1 Study Design

This study will be an open label, single arm, Phase IIA safety and tolerability study to describe the toxicity profile of ribociclib in combination with an aromatase inhibitor in patients aged 70 and older with hormone receptor positive metastatic breast cancer. We plan to study 40 evaluable participants. Participants that receive one dose of treatment will be considered evaluable, anyone that does not receive treatment will be replaced. We plan to stratify based on age such that at least 20 participants are aged 75 years or older. There will be one interim analysis after 20 participants have completed one cycle of the drug.

13.1.1 Primary Objective:

To estimate the safety and tolerability of the combination of ribociclib and an aromatase inhibitor in adults age 70 or older with hormone receptor positive metastatic breast cancer

13.1.2 Secondary Objectives:

1. To describe the full toxicity profile including all grades
2. To estimate the rate of worst grades of myelosuppression (neutropenia, leukopenia, thrombocytopenia, and anemia), neutropenic fever, GI side effects (nausea, diarrhea, decreased appetite, vomiting, stomatitis), fatigue, neuropathy, and thromboembolism
3. To describe rates of dose reductions, dose holds, and hospitalizations
4. To estimate objective response rate and clinical benefit rate as defined by modified RECIST (1.1) criteria
5. To estimate median progression-free and overall survival
6. To determine average plasma steady-state ribociclib C_{trough} concentrations in patients over the age of 70 years

13.1.3 Exploratory Objectives

7. To estimate the rate of adherence to ribociclib
8. To explore factors other than chronologic age that can affect toxicity rates as identified using a cancer-specific geriatric assessment
9. To describe the results of the Was It Worth It (WIWI) and Overall Treatment Utility (OTU) Questionnaires

13.1.4 Primary Endpoints

The primary endpoint is the incidence of grade 2 and above toxicities attributed (possible or above) to ribociclib.

13.1.5 Secondary Endpoints

1. All toxicities associated with the combinations as measured by NCI CTCAE v.4.0
2. Dose reductions
3. Dose holds
4. Hospitalizations
5. Response as determined by RECIST criteria
6. Progression free survival defined as the time from start of treatment to the first of the following disease events: local/regional/distant recurrence, invasive contralateral breast disease, second primary or death due to any cause
7. Overall survival defined as the time from start of treatment to death due to any cause
8. To determine average plasma steady-state ribociclib C_{trough} concentrations in patients over the age of 70 years

13.1.6 Exploratory Endpoints

1. Adherent to ribociclib will be defined as taking 19/21 pills (90%) of their dose of ribociclib.
2. Toxicity Risk Score
3. WIWI response
4. OTU response

13.2 Sample Size and Accrual Rate

Given a sample size of 40 evaluable subjects the half-width of the 95% confidence limits for the rate of grade 2 or higher toxicities will be less than or equal to 0.16. For example if we saw a toxicity rate of 0.5 (20 subjects/40) the 95% lower and upper confidence limits would be 0.34 and 0.66, respectively. Further a sample size of 40 will allow us to see a toxicity with a true rate equal to 0.05 in 87 out of 100 trials.

13.3 Interim Analyses

After approximately 20 subjects have completed at least one full cycle of treatment, the study team will review the data (including the toxicity profile, rates of dose reduction, holds and hospitalizations) and assess if the dose being studied is too high, requiring too many patients, in the opinion of the team, to experience a dose reduction. If so, a reduction of the dose will be considered, otherwise the study will continue to completion at the planned dose.

13.4 Analysis Plan

Rates and associated 95% exact Clopper and Pearson binomial confidence limits will be estimated for 1) grade 2 or higher other toxicities, and 2) dose reductions, dose holds and hospitalizations, and 3) objective response rate (CR+PR) and clinical benefit rate (CR+PR+SD) as determined by RECIST. Progression free survival and overall survival will be estimated using the product limit method of Kaplan and Meier/ Cox proportional hazards methods.

Tables will be created to summarize the toxicities and side effects by age strata, course, organ, severity and attribution for all patients. Descriptive statistics will be provided for study participant demographics, number of drug cycles completed, responses from the WIWI Questionnaire and the OTU by age strata and overall. General linear models and graphical methods will be used to explore factors as identified by a cancer-specific geriatric assessment that may be predictive of toxicity/dose reduction, dose holds or hospitalizations.

The relationship between plasma trough and percent drop in neutrophil and platelet counts will be analyzed used linear models methods.

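### Section 13.4 names a normal-error linear model for outcomes it otherwise treats as per-patient proportions; this exploratory analysis should name a binomial model

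*Combined protocol and SAP*

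**What the plan says.** Section 13.4 (Analysis Plan) states: "General linear models and graphical methods will be used to explore factors as identified by a cancer-specific geriatric assessment". It describes the factors sought as ones "that may be predictive of toxicity/dose reduction, dose holds or hospitalizations". The Analysis Plan paragraph of the synopsis repeats the method. Neither place gives a link function, an error distribution, an outcome coding or a list of factors.

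The analysis serves an exploratory objective in section 13.1.3: "To explore factors other than chronologic age that can affect toxicity rates as identified using a cancer-specific geriatric assessment".

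The opening paragraph of section 13.4 handles the same outcomes differently: "Rates and associated 95% exact Clopper and Pearson binomial confidence limits will be estimated for". The list that follows there covers toxicity of grade 2 or higher, dose reductions, dose holds and hospitalizations. The primary endpoint in section 13.1.4 is likewise an incidence: "The primary endpoint is the incidence of grade 2 and above toxicities attributed (possible or above) to ribociclib".

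**The concern.** Exact binomial limits presuppose one yes/no result per patient. A general linear model presupposes a roughly continuous outcome with constant error variance. For a yes/no outcome the variance is p(1−p): 0.593 × 0.407 = 0.241 for a patient at risk 0.593, but 0.95 × 0.05 = 0.0475 at risk 0.95. A straight line is also not confined to 0–1. A plot or table of risk against a geriatric score could therefore show risks above 100% or below 0%, with intervals that cannot be reported.

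Many of the geriatric measures in Appendix F are scores or continuous values: the ten-item physical functioning scale, the 17-item mental health scale, the 12-item social support survey, Timed Up and Go in seconds, the 0–28 cognition score, BMI and percent weight loss. The continuous-factor case is thus a realistic one. At stake is how usable the risk estimates for the geriatric objective would be.

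**Working it through.** **The plan's own figures.** Section 13.2 gives none for the regression, only for the binomial analysis: "Given a sample size of 40 evaluable subjects", with 20 events of 40, "the 95% lower and upper confidence limits would be 0.34 and 0.66, respectively". Clopper–Pearson for 20/40 gives 0.338 to 0.662, half-width 0.162, which matches after rounding. The plan also says 40 patients will "allow us to see a toxicity with a true rate equal to 0.05 in 87 out of 100 trials"; 1 − 0.95^40 = 0.871, which matches. Both figures treat toxicity as one yes/no per patient.

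**Inputs.**
- N = 40 (section 13.2).
- Event rate 0.593: grade 3–4 neutropenia in the earlier ribociclib–letrozole trial, (166 + 32)/334 (Table 2.4.1a).
- Event rate 0.811: any grade 3 or 4 adverse event, all causes, (221 + 50)/334 in the same table. This assumes the two columns are exclusive worst grades.
- Event rates 0.90 and 0.95: my assumptions. The plan states no expected rate for grade 2 or higher attributed toxicity.
- Odds ratios of 1, 2 and 3 per SD of a standard normal score, and of 1 and 3 for a binary factor with 30% prevalence: my assumptions.

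**Method.** The true model is logit P(Y=1) = a + ln(OR)·x, with a set to give the stated overall rate. Ordinary least squares of Y on x was fitted in 4,000 simulated trials per cell. Trials with a constant outcome were dropped (about 13% at rate 0.95; 0.95^40 = 0.129). Monte Carlo error on a share near 50% is about 1.96 × √(0.25/4000) = 1.5 percentage points.

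**Results, continuous factor (OR 1 / 2 / 3).**

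| Event rate | Any fitted risk outside 0–1 | Any 95% interval for a fitted risk outside 0–1 | Coverage of slope interval |
|---|---|---|---|
| 0.593 | 4 / 36 / 69% | 86 / 98 / 100% | 94.6 / 96.8 / 98.0% |
| 0.811 | 20 / 58 / 84% | 100 / 100 / 100% | 94.5 / 94.1 / 94.2% |
| 0.90 | 38 / 64 / 84% | 100 / 100 / 100% | 94.4 / 92.6 / 87.8% |
| 0.95 | 51 / 68 / 83% | 100 / 100 / 100% | 95.0 / 93.0 / 91.5% |

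The problem mirrors at low rates, where fitted risks fall below 0: at a rate of 0.20 the share with an out-of-range fitted risk was 17 / 59 / 84%.

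**Results, single binary factor.** No fitted risk left 0–1 in any cell. This is algebraic: the two fitted values are the two group proportions. Intervals for fitted risks left the range in 25–100% of trials. Slope coverage was 95–97%.

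**Slope tests.** With no true effect (OR 1), the rejection rate at the 5% level was 3.6–5.8% across all cells.

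**What a binomial model would face.** Fitted risks stay within 0–1 by construction. The limit becomes the number of patients without the event, 40(1 − p): 16.3 at 0.593, 8 at 0.80, 4 at 0.90, 2 at 0.95. At 10 per coefficient (a rule of thumb, my assumption) these support 1.6, 0.8, 0.4 and 0.2 coefficients. That argues for one factor at a time and for penalised or exact estimation.

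**The case against.** The best case against the point has five parts.

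1. *Error bars and factor selection.* A reader might infer that the standard errors are invalid and would mislead about which factors predict toxicity. The simulation does not support that. Type I error is near 5% everywhere, and slope coverage is 94–98% up to a rate of 0.811. The objective concerns which factors matter, which is a question about slopes, and the plan does not promise predicted risks. This stands. The weakness lies mainly in fitted risks and their intervals.

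2. *Event rates.* A reader might infer that high rates are expected for all four outcomes. The documents give background rates for toxicity only. Dose holds have indirect support, because Table 6.2.2a calls for a hold at grade 3 or 4 neutropenia. Nothing is given for dose reductions or hospitalizations. This stands too, although the low-rate mirror means an uncommon outcome does not escape the problem.

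3. *Outcome coding.* Yes/no coding is an inference. Holds and hospitalizations could be counts, toxicity could be a grade, and section 13.1.6 lists an undefined toxicity risk score. *General* may also be a slip for *generalized*; the next paragraph of section 13.4 uses plain linear models for the blood-count outcomes. The text cannot settle this. On any of these readings the wording still needs completing.

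4. *Sparsity.* Few non-events are a limit of 40 patients, and logistic regression meets the same limit. True; the change removes impossible risks but does not add precision.

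5. *Consequence.* The objective is exploratory, graphical methods are planned alongside the model, and no decision rule uses it. True.

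**Conclusion.** The point holds as a modest one. The plan names a normal-error model for outcomes that its own section otherwise treats as binomial, and it names no binomial alternative. With a continuous geriatric score and an odds ratio of 2–3 per SD, out-of-range fitted risks would be expected in roughly a third to two thirds of trials at a rate of 0.593 and in 58–84% at 0.811 to 0.95. Intervals for fitted risks would nearly always leave 0–1. With a single binary factor the fitted risks stay in range. Clear under-coverage of slopes needs both a strong continuous factor and a rate of 0.90 or more.

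These sizes rest on the assumed odds ratios, a normally distributed score, a logistic truth and yes/no coding. The 0.90 and 0.95 rates are assumptions, and 0.811 depends on how the adverse-event table is read. The primary rate and its Clopper–Pearson limits do not depend on this model.

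**What to change.** In section 13.4 and the synopsis, replace the general linear model with logistic regression (a generalized linear model with a binomial outcome). State that:

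- each outcome is coded yes/no per patient;
- geriatric factors are examined one at a time;
- Firth penalisation or an exact method is used where events or non-events are few. Using Firth throughout would avoid having to set a threshold;
- an outcome seen in all patients or in none is only described.

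The planned graphics can stay. Ordinal regression on worst attributed grade may be listed as an optional sensitivity analysis, no more: its proportional-odds assumption is hard to check in 40 patients. If a generalized model was intended all along, the same edit records it.

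The cost is a few lines of text and slightly more analysis work, with no change to data collection or sample size. Estimates will remain imprecise, with about 8, 4 or 2 non-events among 40 at rates of 0.80, 0.90 or 0.95, and the report should say so.

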14. DATA HANDLING, DATA MANAGEMENT, RECORD KEEPING

14.1 Source Documents

Source documents are original documents, data, and records (e.g., medical records, pharmacy dispensing records, recorded data from automated instruments, laboratory data) that are relevant to the clinical trial. The Site Investigator or their designee will prepare and maintain adequate and accurate source documents. These documents are designed to record all observations and other pertinent data for each patient enrolled in this clinical trial. Source documents must be adequate to reconstruct all data transcribed onto the case report forms.

14.2 Data Capture Methods and Management

Data for this trial will be collected using Medidata RAVE, City of Hope's electronic capture system. Medidata RAVE is a web based, password protected system that is fully compliant with global regulatory requirements, including 21CRF Part 11 compliant.

Study personnel at each site will enter data from source documents corresponding to a subject's visit into the protocol-specific electronic Case Report Form (eCRF).

14.3 Case Report Forms/Data Submission Schedule

Study personnel at each site will enter data from source documents corresponding to a subject's visit into the protocol-specific electronic Case Report Form (eCRF) when the information corresponding to that visit is available.

The investigator is responsible for all information collected on subjects enrolled in this study. All data collected during the course of this study must be reviewed and verified for completeness and accuracy by the investigator. All case report forms must be completed by designated study personnel. The completed case report forms must be reviewed, signed and dated by the Site Investigator or designee in a timely fashion.

All data will be collected using the electronic data collection system described in [Section 14.2](#), and will be submitted according to the timelines indicated in [Table 14.3](#).

Table 14.3: Data Submission Schedule

Form	Submission Timeline
Eligibility Checklist	Complete prior to registration
On Study Forms	Within 14 calendar days of registration
Baseline Assessment Forms	Within 14 calendar days of registration
Treatment Forms	Within 14 calendar days of treatment administration
Adverse Event Report Forms	Within 14 calendar days of the study visit
Response Assessment Forms	Within 10 calendar days of the response assessment
Other Assessment Forms (concomitant medications, chemistry, hematology etc.)	Within 10 calendar days of the assessment
Off Treatment/Off Study Forms	Within 10 calendar days of data collection

14.4 Regulatory Records

The investigator will maintain regulatory records, including updating records in accordance with Good Clinical Practice guidelines and FDA regulations. Additional information regarding required documents is provided in the DCC Operations Manual, a supplement to this protocol.

15. ETHICAL AND REGULATORY CONSIDERATIONS

15.1 Ethical Standard

This study will be conducted in conformance with the principles set forth in *The Belmont Report: Ethical Principles and Guidelines for the Protection of Human Subjects of Research* (US National Commission for the Protection of Human Subjects of Biomedical and Behavioral Research, April 18, 1979) and the Declaration of Helsinki.

15.2 Regulatory Compliance

This study is to be conducted in compliance with the IRB approved protocol and according to the following considerations:

- US Code of Federal Regulations (CFR) governing clinical study conduct
 - Title 21 Part 11 – Electronic Records; Electronic Signatures
 - Title 21 Part 50 – Protection of Human Subjects
 - Title 21 Part 54 – Financial Disclosure by Clinical Investigators
 - Title 21 Part 56 – Institutional Review Boards

- Title 21 Part 58 – Good Laboratory Practice for Nonclinical Laboratory Studies
- Title 21 Part 312 – Investigational New Drug Application
- Title 45 Part 46 – Protection of Human Subjects
- US Federal legislation, including but not limited to
 - Health Insurance Portability and Accountability Act of 1996
 - Section 801 of the Food and Drug Administration Amendments Act
- Applicable state and local laws. For research occurring in California, this includes but is not limited to State of California Health and Safety Code, Title 17
- Applicable institutional research policies and procedures

15.3 Institutional Review Board

In accordance with City of Hope policies, an Institutional Review Board (IRB) that complies with the federal regulations at 45 CFR 46 and 21 CFR 50, 56 and State of California Health and Safety code, Title 17, must review and approve this protocol and the informed consent form prior to initiation of the study. All institutional, NCI, Federal, and State of California regulations must be fulfilled.

Any documents that the IRB may need to fulfill its responsibilities (such as protocol, protocol amendments, Investigator's Brochure, consent forms, information concerning patient recruitment, payment or compensation procedures, or other pertinent information) will be submitted to the IRB. The IRB's written unconditional approval of the study protocol and the informed consent document will be in the possession of the Investigator. The Investigator will obtain assurance of IRB/IEC compliance with regulations.

The IRB will be informed of revisions to other documents originally submitted for review; serious unexpected or unanticipated adverse experiences occurring during the study, and any additional adverse experiences in accordance with the standard operating procedures and policies of the IRB; new information that may affect adversely the safety of the patients of the conduct of the study; an annual update and/or request for re-approval; and when the study has been completed.

Any amendment to the protocol document and accompanying informed consent document/template, as developed and provided by the Study PI, will require review and approval by the IRB before the changes are implemented in the study. The protocol and consent will be reviewed and approved by the COH IRB before submission to a participating site IRB.

15.4 Informed Consent

The Principal Investigator or IRB approved named designate will explain the nature, duration, purpose of the study, potential risks, alternatives and potential benefits, and all other information contained in the informed consent document. In addition, they will review the experimental subject's bill of rights and the HIPAA research authorization form. Research subjects will be informed that they may withdraw from the study at any time and for any reason without prejudice, including as applicable, their current or future care or employment at their hospital or any relationship they have with their hospital.

After the study has been fully explained, written informed consent will be obtained from either the patient or his/her guardian or legal representative before study participation. The method of obtaining and documenting the informed consent and the contents of the consent must comply with the ICH-GCP and all applicable regulatory requirements.

Before implementing any study procedure, informed consent shall be documented by the use of a written consent form approved by the IRB/IEC and signed and dated by the patient or the patient's legally authorized representative at the time of consent. A copy of the signed informed consent will be given to the patient or patient's legally authorized representative. The original signed consent must be maintained by the Site Investigator and available for inspection sponsor designated representatives, or regulatory authority at any time.

Informed consent is a process that is initiated prior to the individual agreeing to participate in the study and continues throughout study participation.

15.5 Participant Withdrawal

Participants may withdraw from the study at any time and for any reason without prejudice. The withdrawal must be documented per institutional policies. The COH DCC should be promptly notified of the change in participant status.

Participant withdrawal may consist of any of the following with regard to study procedures and data collection:

- Withdrawal from study treatment, but agreement to continue with active study procedures (safety visit) and chart review and survival follow-up.
- Withdrawal from study treatment and all active procedures, but agreement for chart review and survival follow-up.
- Withdrawal from study treatment, all active procedures, and any future data collection.

Participants who agreed to the collection of research blood samples may withdraw consent to use their specimens, if they are not yet processed as detailed in the consent form. Once the PI is notified of this withdrawal of informed consent, the research specimens will not be used in any research. At that time, any of the existing specimens will be destroyed.

